#### 9.4.5.1 Poolability by Gender Analysis

- Deomographics data will be summarized by gender
- Q statistic will be used to compare the primary effectiveness and safety endpoints by gender. A p-value of < 0.15 will be considered statistically significant for an assessment of poolability by gender. The poolability analyses will be conducted in the PP population for primary effectiveness endpoint and will be conducted in the safety population for primary safety endpoint. If the test result is significant, the 90% exact confidence intervals will be constructed around the percentages of primary endpoints by gender.

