Historically, women have been underrepresented in or excluded from many clinical studies, leading to lack of information for women and their physicians regarding the risks and benefits of many medical treatments and diagnostic procedures. It is the Sponsor's intent to apply the principles from FDA's guidance titled Evaluation of Sex-Specific Data in Medical Device Clinical Studies in this clinical trial to ensure adequate representation of women and minorities. The Sponsor will take reasonable steps to ensure adequate representation of women and racial or ethnic minorities in this clinical trial:

In order to reflect the gender ratio of the intended population, Sponsor plans to enroll approximately 70% males and 30% females in the study. The gender ratio (male: female = 7:3) undergoing ablation procedures in the AF population is estimated based on previous studies. In order to ensure that an appropriate gender ratio is maintained at our sites the sponsor may choose to do the following:

- Target investigational sites where recruitment of needed populations can be more easily facilitated (e.g., women's clinics).
- Alternative communication strategies for study recruitment to reach women through social media ads, study related flyers and brochures may be done.
- The sites will maintain screening logs that can be evaluated to ensure appropriate enrollment of women.
- The investigational sites will be encouraged to increase recruitment by communicating the study information with primary care and family practitioners.
- The subjects may be provided compensation to cover transportation costs and child care costs.

- The investigational sites will be encouraged to consider flexibility in follow-up visit scheduling to match subjects' schedules, which may include evenings and weekends, as long as the visits fall within visit window.
- The sponsor will ensure collection, analysis and reporting of gender demographics in interim post-approval study status reports and clinical study reports.

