#### **5.1.2** Primary Safety Endpoint

The primary safety endpoint is the proportion of subjects with any primary adverse event (PAE) occurring within 7 days following an AF ablation procedure (including the initial and repeat procedures) using the STSF/ST catheter with EPU, except atrio-esophageal fistula and PV stenosis , which may also be considered as primary adverse events if occurring greater than 7 days post the ablation procedure. The PAE rate will be compared against the performance goal of 14%.

The final analyses for primary safety endpoint will apply Bayesian methods and use a beta-binomial model .

The hypotheses to be tested for this evaluation are:

$$H_0: q \ge 0.14$$
 vs.  $H_A: q < 0.14$ 

where q is the PAE rate.

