#### 6. LEVEL OF SIGNIFICANCE

The type I error for the interim and final analyses of the primary endpoints is controlled at one-sided 5%.

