#### 8. SAMPLE SIZE JUSTIFICATION

The final analyses for primary safety and effectiveness endpoints will apply Bayesian methods and use a beta-binomial model .

The power calculations for the Bayesian adaptive design are presented in the simulation report Appendix B Table 6 (probability of success). Under the assumption of 65% success rate for primary effectiveness and 8% rate for primary safety, with 330 subjects, assuming 10-15% attrition rate, we will have more than 90% power for declaring success for each of the primary endpoints controlling the type-I error at 5%.

The total of 330 enrolled subjects includes 280 subjects who will be treated using STSF catheter with EPU and 50 subjects be treated using ST catheter with EPU. Approximately 30 subjects may be excluded or discontinued before receiving treatment assuming 10-15% attrition rate.

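### Confidence intervals for the primary endpoints by sex are produced only if a Q test gives p < 0.15, so they would be missing in a sizeable share of trials with a real difference

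*SAP*

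**What the plan says.** SAP 9.4.5.1 covers sex. Demographics are summarised by gender, and a Q statistic compares the primary effectiveness and safety endpoints. The threshold is explicit: "A p-value of < 0.15 will be considered statistically significant for an assessment of poolability by gender". Interval estimates depend on that result: "If the test result is significant, the 90% exact confidence intervals will be constructed around the percentages of primary endpoints by gender".

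SAP 9.4.5 handles the other subgroups differently. Age, prior drug class, repeat procedure, operator experience, Tag Index segments, contact force and ablation targets each get the number, the percentage and an exact 95% interval. A test is run as well, but nothing depends on it. Sex is not in that list.

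SAP 9.4.6 includes gender as a covariate in logistic regression, but only for the effectiveness endpoint.

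Protocol section 5 states an intent "to apply the principles from FDA's guidance titled Evaluation of Sex-Specific Data in Medical Device Clinical Studies" and gives the expected mix: "Sponsor plans to enroll approximately 70% males and 30% females in the study".

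**The concern.** Making an interval depend on a significance test is selective reporting by rule. With roughly 90 women and few events, the Q test has limited power. A non-significant result would therefore often mean too little information, not similar rates, and that is when an interval is most useful to the reader. When the test is significant, the observed difference has been selected for being large.

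The gap matters most for safety, where no other analysis in the SAP gives the PAE rate in women with its uncertainty. The protocol singles sex out as a factor needing attention, yet the SAP gives it less complete reporting than operator experience or contact force.

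**Working it through.** **Inputs**
- Planning rates and enrolment: "Under the assumption of 65% success rate for primary effectiveness and 8% rate for primary safety, with 330 subjects" (SAP section 8).
- Attrition: "Approximately 30 subjects may be excluded or discontinued before receiving treatment assuming 10-15% attrition rate" (SAP section 8).
- Sex split 70:30 (Protocol section 5); safety performance goal 14% (SAP 5.1.2); Q-test level 0.15 (SAP 9.4.5.1).
- Sex-specific event rates: not in the documents, so assumed. The first two PAE scenarios below are close to the 8% planning rate overall: (0.11 × 89 + 0.07 × 208)/297 = 8.2% and (0.12 × 89 + 0.06 × 208)/297 = 7.8%.

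**Step 1. The plan's own figure.** The SAP claims more than 90% power for each primary endpoint. Applying the final-analysis rules of SAP 9.4.1 to 300 treated subjects and ignoring the interims, safety succeeds with at most 31 PAEs (power 94.0% at 8%), and effectiveness succeeds with at least 167 responders (power 99.97% at 65%). With 280 subjects the powers are 93.7% and 99.95%. The claim is reproduced. No power is stated for the Q test by sex.

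**Step 2. Numbers by sex.** With 10% attrition, 330 × 0.90 = 297, which is 0.70 × 297 ≈ 208 men and 0.30 × 297 ≈ 89 women. With 300 treated, it is 210 men and 90 women.

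**Step 3. The test.** The SAP does not say which form of Q is meant. The pooled form is

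Q = (p_w − p_m)² / [p(1 − p)(1/n_w + 1/n_m)], with p the pooled proportion,

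referred to chi-square with 1 df. The critical value at 0.15 is 2.07.

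**Step 4. How often the intervals appear.** Exact enumeration of two independent binomials, pooled Q, 208 men and 89 women:

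| Assumed true rates, men vs women | Produced | Missing |
|---|---|---|
| PAE 7% vs 11% | 39% | 61% |
| PAE 6% vs 12% | 61% | 39% |
| Effectiveness 68% vs 58% | 59% | 41% |
| Effectiveness 67% vs 60% | 40% | 60% |

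The next rows use 210 men and 90 women. The range covers three forms of Q: pooled, inverse-variance on the risk scale and inverse-variance on the logit scale.

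| Assumed PAE pattern | Produced | Missing |
|---|---|---|
| Men 8%, women at the 14% goal | 51-55% | 45-49% |
| Overall 8%, 1.5-fold excess in women | 31-35% | 65-69% |
| Overall 8%, 2-fold | 58-63% | 37-42% |
| Overall 8%, 3-fold | 89-91% | 9-11% |

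At an overall rate of 8%, the chance of an interval reaches one half at an excess of about 1.8-fold. If the overall rate is lower, a doubling gives an interval in only 42-49% of trials at 5%, and 35-43% at 4%.

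**Step 5. Selection.** With true PAE rates of 7% and 11%, the mean observed difference among trials with a significant test is about 7.5 points, against a true 4. With effectiveness of 67% and 60%, a true 7 points becomes about 12.7.

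**Step 6. An example.** Take 10/89 PAEs in women (11.2%) and 15/208 in men (7.2%). The pooled rate is 25/297 = 8.4%, so Q = 0.0402² / [0.0842 × 0.9158 × (1/89 + 1/208)] = 1.31 and p = 0.25. No interval is constructed. The exact (Clopper-Pearson) 90% interval for women is 6.2% to 18.3%, which includes the 14% goal.

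**The case against.** Several points on the other side are sound.

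- **Only the interval is conditional.** A reader might infer that the plan leaves women without any estimate. It does not go that far: the Q test is always run and needs the counts by sex, and anyone with the counts can compute the exact interval. What stands is that no sentence in 9.4.5.1 commits to reporting those counts and percentages when the test is not significant.
- **The intervals would not usually be missing.** That depends on the assumed excess. For a doubling at the planning rate they appear in about 60% of trials, and for a tripling in about 90%.
- **Effectiveness is partly covered.** SAP 9.4.6 fits a univariate logistic model for gender whatever the Q test shows. It models the sex effect and gives no rate with an interval for each sex, but it is not conditional. The gap is complete only for safety.
- **Sex-specific outcomes are not a study objective.** Protocol section 5 ties the guidance to adequate representation, and its explicit reporting commitment is for gender demographics. It cites a survey on gender and tamponade only for the enrolment ratio. The survey's results are not in the documents, so it cannot support a presumed excess in women.
- **The example depends on the men's count.** With 10/89 in women, the interval is produced if men have 13 or fewer PAEs in 208. That happens in 40% of trials at a male rate of 7%, but in 63% at 6%.
- **An interval that includes 14% is not a failure in women.** The plan sets no goal by sex, and even 7/90 (7.8%) gives 3.7% to 14.1%. The example shows imprecision, which is what the omitted interval would have told the reader.

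None of this gives a reason to keep the condition.

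**Conclusion.** The concern holds as a reporting defect. SAP 9.4.5.1 makes the sex-specific intervals depend on a significance test, unlike SAP 9.4.5 for its listed subgroups, and no other section supplies a safety interval by sex.

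With about 300 treated and a 70:30 split, the intervals would be missing in about 61% of trials for PAE 7% in men vs 11% in women, about 39% for 6% vs 12%, and about 45-49% for 8% vs 14%. When they do appear, the observed difference tends to be too large. These figures rest on assumed sex-specific rates and on the planned sex mix being achieved. The conclusion is the same for all three forms of Q tried.

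A reader might also infer that the trial's conclusions are at risk. The documents do not support that: the performance-goal tests, their thresholds and type I error control do not use this analysis. The issue is confined to supplementary reporting. It is still worth correcting, because the present rule withholds intervals when the data are inconclusive.

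**What to change.** In SAP 9.4.5.1, delete the condition on the test result. State that, for both primary endpoints and whatever the Q-test p-value, the report gives by sex the count, the percentage and the exact 90% interval, plus the female-male difference with its interval. Use the populations already named there: per protocol for effectiveness, safety population for PAEs. Keep the Q test as a supplement and state which form will be used.

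The cost is one amended SAP sentence and one table. No new data, subjects or changes to the primary analysis are needed.

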#### 9.4.5.2 Poolability by Study Sites

To assess the site effect on primary endpoints visually, the success rate at each site will be ploted against the number of subjects from the sites in the PP population. The PAE rate at each site will also be ploted against the number of subjects from the site in the safety population. Any site that appears outlying from general pattern of the rest of sites will be investigated.

- Sites with less than five enrolled subjects will be combined together within their corresponding geographic region in the subgroup analysis so that the combined center(s) will have five or more enrolled subjects. The geographic regions of the U.S. are defined for this analysis as follows: Northeast, Southeast, Great Lakes, Central, and West.
- Q statistic will be used to examine the poolability across sites for the primary effectiveness and safety endpoints. A p-value of <0.15 will be considered statistically significant for an assessment of poolability across the treatment sites. The poolability analyses will be conducted in the PP population for primary effectiveness endpoint and will be conducted in the safety population for primary safety endpoint.

If the sites are not poolable, DerSimonian and Laird non-iterative random effects model  will be used to estimate the overall treatment effects (primary effectiveness and safety endpoints) as well the 90% confidence intervals treating sites as random effects.

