#### 5. TREATMENT DESCRIPTION

The Sponsor's intention is for the enrolled subject population to be as representative as possible of the well-defined study population. Investigators will be encouraged to consecutively evaluate all paroxysmal AF candidates for ablation for participation in the study, and to offer enrollment to all who meet preliminary eligibility criteria. Screening log will be maintained at the research sites.

Sponsor will attempt to include a diversified group of research sites engaging a variety of academic and private institutions geographically located throughout the US. To ensure generalizability of results and minimize the influence of any single site, no more than approximately 15% of the total enrollment will be allowed at a single site. Prior to enrollment, a few sites will be selected to only enroll subjects who will be treated with the ST catheter and the remaining sites will only enroll subjects who will be treated with the STSF catheter.

Potential clinical sites and investigators will be screened on the following criteria:

- Experience and qualifications- Electrophysiologists with Catheter ablation experience, Previous clinical research study experience, performance and reporting,
- Previous experience with hosting and responding to FDA inspections and sponsor audits and their outcomes if applicable
- Study specific: THERMOCOOL SMARTTOUCH® and THERMOCOOL SMARTTOUCH® SF catheter use and past experience, VISITAG module experience

- Patient population: number of patients with Paroxysmal atrial fibrillation, monthly PAF ablation volume.
- Time and resources to commit to the study- Number of ongoing PAF trails, Number of other studies being conducted, number of dedicated study coordinators, number of operators (EPs performing catheter ablation at a site), number of research managers.
- Previous experience with the site enrollment, if any
- Assess if potential Investigators are disqualified, debarred or restricted from performing research by regulatory bodies and/or health authorities.
- Assess financial conflict of interest assessment for investigators and sites
- Certifications and training- GCP, HIPAA, Safe harbor, use of human subjects for research
- IRB processes:
  - Is the site using a central or local IRB?
  - Average turnaround time for full IRB approval?
- Facilities: Esophageal temperature monitoring, equipped to handle emergency situation
- Geographic location: to ensure generalizability

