#### 1. STUDY DESIGN

The SURPOINT COA study is a prospective, multicenter, non-randomized clinical evaluation of the VISITAG SURPOINT Module with EPU when used with the THERMOCOOL SMARTTOUCH® SF catheter (STSF) catheters or the THERMOCOOL SMARTTOUCH® (ST) catheter in treating subjects with symptomatic paroxysmal atrial fibrillation (PAF) who have failed at least one antiarrhythmia drug. A maximum of 330 subjects will be enrolled across up to 45 sites. Two hundred eighty (280) subjects will be treated using the STSF catheter with EPU and 50 subjects will be treated using the ST catheter with EPU. A few sites will be selected to enroll subjects to be treated only with the ST catheter. The remaining sites will enroll subjects to be treated with the STSF catheter. Two interim analyses are planned to take place after all subjects who are treated using the STSF catheter with EPU have completed their 3-month and 6-month follow-up visits for the evaluation of early success. The planned interim analysis will be based on data collected only in the subjects who are treated using STSF catheter with EPU. The final analysis of the primary effectiveness and safety endpoints will be based on all subjects's full 12-month follow-up data. Effectiveness and safety endpoints defined in association with the primary study objectives will be compared to the predetermined performance goals.

Enrolled subjects who satisfy all eligibility criteria will undergo the ablation procedure with the catheters and VISITAG SURPOINT Module. After the study ablation procedure, subjects will enter a 3-Month blanking period (Day 0-90). After the blanking period, subjects will enter the evaluation period (Days 91-365). Subjects having AF recurrence and/or receiving therapeutic interventions during the evaluation period will be considered effectiveness failures.

All subjects will undergo follow up visits at defined intervals (refer to Table 5-1 Schedule of Treatments and Evaluations in protocol). Subjects complete the SURPOINT COA study after the 12-month follow up visit.

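### The random-effects re-estimate of the PAE rate when sites are not poolable (SAP 9.4.5.2) is unreliable at the planned site sizes, and three choices that set the direction of its bias are not stated

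*SAP*

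**What the plan says.** SAP 9.4.5.2 tests whether sites can be pooled with a Q statistic: "A p-value of <0.15 will be considered statistically significant for an assessment of poolability across the treatment sites". Small sites are merged first: "Sites with less than five enrolled subjects will be combined together within their corresponding geographic region", so that each unit has at least five enrolled subjects. The consequence of a significant test is then given: "If the sites are not poolable, DerSimonian and Laird non-iterative random effects model" is to estimate the overall effect for both primary endpoints, "as well the 90% confidence intervals treating sites as random effects".

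The section does not say whether site rates enter as raw proportions or on a transformed scale, how a site with no events is weighted, or which Q statistic is meant.

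The design around it: "A maximum of 330 subjects will be enrolled across up to 45 sites" (SAP 1); "Approximately 30 subjects may be excluded or discontinued before receiving treatment" (SAP 8); "no more than approximately 15% of the total enrollment will be allowed at a single site" (Protocol 5). On the safety goal, SAP 5.1.2 states: "The PAE rate will be compared against the performance goal of 14"%. SAP 9.4.1 decides trial success only by two posterior-probability rules: above 0.97 for effectiveness over 50%, and above 0.95 for a PAE rate below 14%.

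**The concern.** DerSimonian-Laird (DL) treats each site's estimate as normal with a known variance and weights it by the inverse of that variance. Here the variance comes from the same few binary outcomes as the rate. On the raw scale, a site with few events looks precise and gets a large weight, which pulls the PAE rate down. A site with none has zero variance and cannot be weighted without a correction. On the logit scale, a site with few events looks imprecise and loses weight, which pulls the rate up.

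This is the only overall re-estimate that the SAP offers once site differences are found. Its 90% level matches the one-sided 5% standard of SAP 6, so readers are likely to set it beside the 14% goal. The sponsor is not blinded to aggregate data (SAP 3), so the open choices could be made with results in view.

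**Working it through.** **Inputs from the documents.** 330 enrolled, up to 45 sites, about 30 lost before treatment, minimum 5 enrolled per unit, site cap about 15%, goals 14% and 50%, planned rates 8% and 65%.

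**Assumed.** 20, 30 or 40-45 sites. Between-site variation from none to an intraclass correlation (ICC) of 0.10, or a logit-scale SD of 0.5.

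**1. The plan's own figures.** The SAP states more than 90% power with 5% type I error. Exact binomial evaluation of the final rules, without interim looks or site variation, at n = 280-300 gives:
- Safety: power 93.4-94.6%, type I error 3.6-4.3%.
- Effectiveness: power above 99.9%, type I error 2.8-3.2%.

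These agree with the SAP. It gives no figure for the DL step.

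**2. Site sizes.** 330/45 = 7.3 enrolled per site; (330 - 30)/45 = 6.7 treated; 300/20 = 15 if there are only 20 sites. At the planned 8%, the chance of no events is 0.92^5 = 66% for a 5-subject site and 0.92^10 = 43% for a 10-subject site.

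**3. Mechanism.** On the raw scale v_i = p_i(1 - p_i)/n_i and w_i = 1/v_i. Then Q = Σw_i(p_i - p_w)², where p_w is the w-weighted mean, and τ² = max{0, [Q - (k - 1)]/[Σw_i - Σw_i²/Σw_i]}. The estimate is Σ[p_i/(v_i + τ²)] / Σ[1/(v_i + τ²)].

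Take three sites of 10 with 0, 1 and 3 events, so the crude rate is 4/30 = 13.3%. This shows direction only.
- Raw, with 0/10 replaced by 0.5/11: rates 0.045, 0.100, 0.300; variances 0.0039, 0.0090, 0.0210; Q = 2.61; τ² = 0.0028. The estimate is 10.1%.
- Logit, same correction: values -3.04, -2.20, -0.85; variances 2.10, 1.11, 0.48; Q = 2.47; τ² = 0.246. The estimate is -1.606, or 16.7%.

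**4. Simulation at a true PAE rate of 14%** (thousands of trials per DL setting). The nominal share of 90% intervals wholly below 14% is 5%. The Pearson Q is Σ(x_i - n_i p)²/[n_i p(1 - p)], with p the pooled rate; the inverse-variance Q is the one in step 3. Ranges run over the assumed site counts and site variation.

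| Form | Trials counted | Mean estimate | Wholly below 14% |
|---|---|---|---|
| Raw, 0.5 at zero-event sites | all | 10.1-11.7% | 34-76% |
| Same | flagged, Pearson Q | about 10-11% | 43-74% |
| Same | flagged, inverse-variance Q | 11.4-14.7% | 0-42% |
| Raw, 0.5 at every site | all | 12.1-12.9% | 13-39% |
| Logit, 0.5 at zero-event sites | all | 16.2-19.2% | 0-0.6% |

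The Pearson row is for unequal site sizes. A set with mostly equal sizes and ICC up to 0.10 gave 54-82%. Dropping zero-event sites makes the share about 0% among flagged trials. At about 7 per site the inverse-variance Q fires in only 0.1-18% of trials, and the share is then 0-4%.

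**5. At the planned 8%**, in Pearson-flagged trials, raw DL with 0.5 at zero-event sites averages 5.5-7.9% and logit DL 11-14%. The logit interval clears 14% in only 2-23% of these trials. A beta-binomial fit clears it in 82-92% when there is no site variation.

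**6. Effectiveness.** At a true 50% the mean is 50.0% in the raw and logit forms, and the interval lies wholly above 50% in 2-6% of trials. At 65%, raw DL gives 66.5-68.0% and logit 62.6-64.0%.

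**7. Alternatives at a true 14%.**
- Beta-binomial with profile-likelihood intervals, Pearson-flagged trials, 20 and 30 sites: 14.0-14.4%, wholly below 14% in 1-3%, coverage 92-95% (250 trials per setting). A further check that included 40 sites gave 14.0-14.2% and 2-3%.
- Random-intercept logistic, 30 sites: 14.3-14.4%; its interval was not checked.
- DL with a common pooled variance p(1 - p)/n_i: 14.0-14.1%, wholly below in about 5-9%.

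**The case against.** The best counter-argument is that any single bias figure belongs to one branch of choices that the SAP leaves open. A reader might infer that a true 14% will be reported as roughly 10.5-11%, with false reassurance in around half of non-poolable trials or more. The documents do not support that. It needs raw proportions, a correction at zero-event sites only, and a Pearson-type trigger. Because DL computes its own inverse-variance Q, that Q is a natural reading of the trigger, and with it the share falls to 0-42%. On the logit scale the error reverses. This objection stands, and it limits what can be claimed to unreliability in a direction not yet fixed.

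A reader might also infer that both primary conclusions, or the trial's type I error, are compromised. They are not. SAP 9.4.1 alone decides success, the DL step sits under subgroup analyses, and no section tests its interval against a goal. At a true 14% the primary safety rule would pass only 3.6-4.3% of the time, so a misleading DL interval would usually appear beside a failed primary result, the exact binomial analysis and the site plots. Effectiveness is not biased at its goal.

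Finally, specifying pooled-variance weights would cure most of the problem without abandoning DL. That is true. It still leaves a normal approximation at about seven subjects per site, when the SAP already uses binomial-likelihood models elsewhere.

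**Conclusion.** The point holds for the supportive PAE estimate. At a true rate of 14%, the method as written could average anywhere from about 10% to about 19%, on either side of the goal, depending on the scale, the zero-event rule and the trigger. The worst false reassurance, about 43-74% of flagged trials against a nominal 5%, belongs to the raw form with a Pearson trigger; with the inverse-variance Q it is about 0-42%. Effectiveness shows no bias at 50% and a shift of about 1-3 points at 65%.

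The result rests on about 300 treated subjects and on assumed site counts (the documents give only a maximum of 45) and between-site variation. It is worth correcting before the analysis, but does not threaten the primary result.

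**What to change.** In SAP 9.4.5.2, replace DerSimonian-Laird with a binomial-likelihood random-site model: a beta-binomial, or a logistic model with a random site intercept. Report the marginal PAE and success rates with profile-likelihood 90% intervals, and name the Q statistic that triggers the step. Sites without events then need no correction. SAP 9.4.6 already plans random site effects in a logistic model for effectiveness when sites are not poolable, so the extension is small.

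The cost is about a sentence of SAP text and a standard procedure, with no change to data or sample size. The downside is a safety interval that is wider and looks less favourable than the one from raw-proportion DL. The beta-binomial has the better-tested interval here; the coverage of the logistic version should be checked if it is chosen.
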